3.2 General study level definitions

3.2.1 Analysis time points

3.2.1.1 Relative day

The relative day of a visit or an event with respect to the first application of study medication will be presented in subject data listings. Relative days will be calculated as follows:

- If the start (stop) date occurred prior to the first application of study medication, the relative day is calculated as start (stop) date minus date of first patch application. That means that in subject data listings, relative days based on this situation will be preceded by a '-'.
This document cannot be used to support any marketing or promotional activities or variations thereof.
- If the start (stop) date occurred on or after the first application of study medication but prior to the last patch removal, the relative day is calculated as start (stop) date minus date of first patch application + 1.

- If the start (stop) date occurred after the date of last patch removal, the relative day is calculated as start (stop) date minus date of first patch application + 1. In subject data listings, relative days based on this situation will be preceded by a '+’.

Relative days will not be presented for partial or missing dates.

3.2.1.2 Date of last patch removal

The date of last patch application is documented on the Study Termination page of the eCRF. If the date of last patch application on this page is missing the last available kit start date on the Drug Accountability log form will be used as the date of last patch application. Thus, the date of the last patch removal is defined as the date of the last patch application + 1.

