6.3.1 Potential drug-induced liver injury IMP discontinuation criteria

Subjects with potential drug-induced liver injury (PDILI) must be assessed to determine if IMP must be discontinued. In addition, all concomitant medications and herbal supplements that are not medically necessary should also be discontinued.

The PDILI criteria below require immediate and permanent discontinuation of IMP:

- Subjects with either of the following:
 - ALT or AST $\geq 5xULN$
 - ALT or AST $\geq 3xULN$ and coexisting total bilirubin $\geq 2xULN$

The PDILI criterion below requires immediate discontinuation of IMP:

- Subjects with ALT or AST $\geq 3xULN$ who exhibit temporally associated symptoms of hepatitis or hypersensitivity. Hepatitis symptoms include fatigue, nausea, vomiting, right upper quadrant pain or tenderness. Hypersensitivity symptoms include fever (without clear alternative cause), rash, or eosinophilia (ie, $>5\%$).

If a nondrug-related cause for the symptoms can be confirmed, these subjects may resume IMP administration after discussion with the responsible UCB physician, but only when the requirements for rechallenge with IMP as provided in [Section 11.6.1.2](#) are followed.

The PDILI criterion below allows for subjects to continue on IMP at the discretion of the investigator.

- Subjects with ALT or AST $\geq 3xULN$ (and $\geq 2x$ baseline) and $<5xULN$, total bilirubin $<2xULN$, and no eosinophilia (ie, $\leq 5\%$), with no fever, rash, or symptoms of hepatitis (eg, fatigue, nausea, vomiting, right upper quadrant pain or tenderness).

Evaluation of PDILI must be initiated as described in [Section 11.6.1](#). If subjects are unable to comply with the applicable monitoring schedule, IMP must be discontinued immediately.

Investigators should attempt to obtain information on subjects in the case of IMP discontinuation to complete the final evaluation. Subjects with PDILI should not be withdrawn from the study until investigation and monitoring are complete. All results of these evaluations and observations, as well as the reason(s) for IMP discontinuation and subject withdrawal (if applicable), must be recorded in the source documents. The eCRF must document the primary reason for IMP discontinuation.

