8.3.3 Visit 9 (Day 106)/End of Maintenance

The following assessments will be performed.

Information and procedures listed below will be collected/completed by the investigator and/or study staff, as appropriate, via a telephone or telemedicine call with the subject/legal representative.

- Withdrawal criteria
- Menstrual function for all female subjects

Assessments listed below will be completed by mobile study personnel at the subject's/legal representative's home and records of the procedures will be obtained, with information noted as part of the subject's study record.

- Brief physical examination, including body weight, height, BMI, and vital signs
- Neurological examination
- 12-lead ECG

For lab collections and procedures listed below, mobile study personnel will be sent to the subject's/legal representative's home. Samples will be prepared and sent to a central laboratory for processing and analysis, and results will be provided to the study site.

- Safety laboratory tests
- Urine pregnancy test for all female subjects
- Hormone status
- PK sampling—record sampling time, time of application of study medication, and application site of study medication in eCRF

Assessments listed below will be completed either by the subject or investigator/trained study staff, as required. Assessments that require interviews will be completed via a telephone or telemedicine call.

- C-SSRS (Since Last Visit version)
- IRLS
- CGI
- RLS-6
- mMIDI
- Subject Quality of Life Questionnaire

Additional assessments and procedures are listed below.

- Recording of medication and procedures: See [Section 8.2.1](#).
- AE assessment: See [Section 8.2.1](#).
- Contact IRT: The IRT will be contacted to obtain study medication kit numbers for the Taper Period.
- Dispense study medication for the Taper Period. See [Section 7.5](#) for the description of the direct-to-subject shipment process for the remote study model.
- Return any unused study medication

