8.6 Withdrawal Visit

Procedures for a withdrawal visit are the same as for Visit 9.

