3.2.2 Study periods

The following time periods are defined for this study.

- Screening Period:

The Screening Period starts with Visit 1 and ends the day before the date of the first patch application. This period includes Visit 2/Day 0 at which the subjects are randomized, and study medication is assigned and shipped.

- Titration Period:

The Titration Period starts at the day of the first patch application (Day 1) and ends on the day prior to Visit 6. In case of a premature withdrawal before Visit 6, the Titration Period ends at the day of the Withdrawal Visit. If the Withdrawal Visit is missing or the date of the last patch removal (or last known patch removal) is before the Withdrawal Visit, the Titration Period ends at the day of last patch removal.

- Maintenance Period:

The Maintenance Period starts at Visit 6 and ends at Visit 9. If the subject withdraws prior to Visit 9, the Maintenance Period ends at the day of the Withdrawal Visit date or the last patch removal date (or last known patch removal date), whichever is earlier.

- Taper Period:

The Taper Period starts at the date of last maintenance patch removal and ends at the day of last patch removal. If the day of last patch removal is on the date of last maintenance patch removal, i.e., no de-escalation was performed for any reason, then no Taper Period is defined for this subject.

- Treatment Period:

The Treatment Period comprises the Titration Period, the Maintenance Period, and the Taper Period, i.e., it starts with the day of first patch application and ends on the maximum end date of the Titration, Maintenance and Taper periods.

- Safety Follow-Up Period:

The Safety Follow-Up Period starts the day after the end of the Treatment Period and ends at the date of the Safety Follow-Up Visit. However, AEs starting within 30 days following the date of last patch removal will be considered for analysis, even if the start date is after the

date of last study assessment. If the subject rolls over into the RL0007 study, then the Safety Follow-up Period dates will be missing.

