10.2 Adverse events

Adverse events will be documented throughout the entire study on an ongoing basis. TEAEs are defined as events that started during the Treatment Period or within 30 days following the end of the Treatment Period (i.e., on or after the date of first patch application and within 30 days following the date of last patch removal) or any unresolved event already present before administration of treatment that worsens in intensity following exposure to the treatment. For AEs with a partial or missing start date, the imputation rules as described in [Section 4.2.2](#) will be applied.

Adverse events with a missing start date are defined as treatment-emergent if the end date of the AE is not on or before the date of first patch application.

An AE with action taken regarding study medication reported on the AE page of the eCRF as “drug permanently withdrawn” will be regarded as an AE leading to discontinuation of study medication.

Adverse events which have the question “Serious Adverse Event?” answered “yes” or missing are considered serious.

Treatment emergent AEs will be tabulated by MedDRA SOC, High Level Term (HLT) and PT. The number and percentage of subjects experiencing each event at least once will be summarized in addition to the number of events. In summaries of TEAEs by relationship and intensity, respectively, the number of events will not be presented.

All summaries will be sorted alphabetically by SOC and HLT and by frequency of events (PT) in the total rotigotine group within HLTs. If there is more than one PT with the same frequency in the total rotigotine group these events will be sorted alphabetically.

An overview of the incidence and frequency of all TEAEs, serious TEAEs, TEAEs leading to discontinuation of study medication, related TEAEs, severe TEAEs, all deaths and TEAEs leading to death will also be provided.

The following tabular summaries will be presented also.

- TEAEs
- TEAEs by intensity
- TEAEs by maximum intensity
- TEAEs by relationship to study medication per the Investigator
- Serious TEAEs
- Serious TEAEs by Relationship to study medication per the Investigator
- non-serious TEAEs above reporting frequency threshold of 5%

Individual subject data listings will be presented for all AEs.

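### When the last patch date is missing, the SAP substitutes the last kit start date, which (if it means first use) dates patch removal too early: 3–4 days with a recorded taper-kit start, about a month in the worst case without one

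*SAP*

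**What the plan says.** SAP 3.2.1.2 takes the last application date from the Study Termination page. If it is missing, "the last available kit start date on the Drug Accountability log form will be used as the date of last patch application". Removal is that date plus one day.

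The removal date is then used for:

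- duration of exposure (SAP 10.1);
- the TEAE window, which takes in events that start "within 30 days following the date of last patch removal" (SAP 10.2);
- the concomitant-medication cutoff (SAP 6.4);
- the validity of IRLS and CGI Item 1 scores, which ends one day after removal (SAP 3.5.4 and 4.2.1);
- the end of Maintenance for a withdrawal, which is the Withdrawal Visit or "the last patch removal date (or last known patch removal date), whichever is earlier" (SAP 3.2.2);
- the plus sign in listings, given "If the start (stop) date occurred after the date of last patch removal" (SAP 3.2.1.1).

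SAP 10.2, 6.4 and 3.5.4 each name both the Treatment Period and the last patch removal, as if the two always ended together. Under SAP 3.2.2 the Treatment Period ends at the latest of the Titration, Maintenance and Taper ends. For a completer that is never before Visit 9.

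On supply, Protocol Table 5-1 dispenses medication at Visits 3, 6, 7, 8 and 9. The Visit 9 list (Protocol 8.3.3) includes "Dispense study medication for the Taper Period", and Protocol 8.6 adds that "Procedures for a withdrawal visit are the same as for Visit 9". SAP 3.2.2 also foresees the case where "no de-escalation was performed for any reason, then no Taper Period is defined for this subject".

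**The concern.** A kit is used over many days. Its start date marks the beginning of that use, whereas the quantity needed is the end. The substitution therefore errs in one direction.

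The ordinary case is mild, because a subject who attends Visit 9 or a Withdrawal Visit should receive a taper kit, and that kit starts close to the end of treatment. The error grows when no taper-kit start is on record. Examples are a subject lost to follow-up or one who stops without de-escalation. Protocol 6.3.1 gives one route to an abrupt stop: "The PDILI criteria below require immediate and permanent discontinuation of IMP".

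At stake are the exposure figure and the completeness of the TEAE and concomitant-medication tables. SAP 7 drops the compliance calculation and refers the reader to the exposure section, so exposure is the main remaining measure of treatment received. Meanwhile SAP 10.1 already uses an eCRF drug dosing log with an end date for each dosing interval, and the fallback ignores it. SAP 3.2.2 also relies on a last known removal date that SAP 3.2.1.2 does not define.

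**Working it through.** **Schedule.** Titration is 3 weeks, Maintenance 12 weeks and Taper 4 days. Visit 6 = 1 + 21 = Day 22; Visit 9 = 22 + 84 = Day 106; end of Taper = 106 + 4 = Day 110. This matches Protocol Table 5-1.

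**Formulas.** Let K be the last recorded kit start, L the true last application, and Day 1 the first patch. From the SAP definitions:

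- removal: K + 1 instead of L + 1;
- exposure in days: (K + 1) − 1 + 1 = K + 1 instead of L + 1;
- TEAE window end, removal wording: K + 31 instead of L + 31;
- last day for a valid score, removal wording: K + 2 instead of L + 2;
- error: L − K days.

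**Assumptions.** Kit start means first use, there is one kit per dispensing visit, and visits fall on nominal days. The documents give neither the kit size nor the number of kits per visit.

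| Situation | K | L | Error | Exposure, fallback vs true | TEAE end, removal wording | Last valid score day under fallback |
|---|---|---|---|---|---|---|
| Taper kit started Day 107 | 107 | 110 | 3 | 108 vs 111 (−2.7%) | 138 vs 141 | 109 |
| Taper kit dated Day 106 | 106 | 110 | 4 | 107 vs 111 (−3.6%) | 137 vs 141 | 108 |
| Withdrawal, no taper-kit start | 50 | 50 | 0 | 51 vs 51 | 81 vs 81 | 52 |
| Same, later stop | 50 | 64 | 14 | 51 vs 65 (−21.5%) | 81 vs 95 | 52 |
| Same, latest stop | 50 | 77 | 27 | 51 vs 78 (−34.6%) | 81 vs 108 | 52 |
| Completer, no taper | 78 | 105 | 27 | 79 vs 106 (−25.5%) | 109 vs 136 | 80 |
| Completer, tapers, no taper-kit start | 78 | 110 | 32 | 79 vs 111 (−28.8%) | 109 vs 141 | 80 |

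**Visit windows, last row.** With the protocol windows, Visit 8 can be on Day 78 − 2 = 76 and Visit 9 on Day 106 + 2 = 108, so the taper ends on Day 112 and the error is 112 − 76 = 36 days. With the wider Visit 8 window in SAP 3.2.3, Visit 8 can be on Day 78 − 5 = 73, and the error is 112 − 73 = 39 days.

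**Taper-kit start recorded.** The Day 106 scores are within the cutoff (Day 108 or 109) and are kept.

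**Withdrawals.** SAP 3.2.2 takes the earlier of Withdrawal Visit and removal, so both wordings of the TEAE window give the same loss. With K = 50 and L = 77, AEs that start during wear (to Day 78) stay inside the window to Day 81, but only Days 79–81, 3 of the 30 post-removal days, are kept. On the face of SAP 6.4, a medication first taken on Days 52–78 is neither prior nor concomitant. A Day 78 Withdrawal Visit score, valid to Day 79 on the true date, fails the Day 52 cutoff.

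**Completer who tapers (last row).** The two wordings part. Under the removal wording the TEAE window closes on Day 109, while patches are worn into Day 111. Under the Treatment Period wording it runs to 106 + 30 = Day 136, against a true Day 141. That wording would also keep the Visit 9 scores (SAP 3.5.4) and medications up to Visit 9 (SAP 6.4). SAP 4.2.1, however, names only last patch removal for scores.

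**The case against.** The strongest case against is that the rule applies only when one eCRF field is blank. No frequency is given, the study stopped early, efficacy is only summarised (SAP 8.1.2), and all data are listed (SAP 3.9). That stands and sets the severity.

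Further points:

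- **Meaning of kit start.** If it is a dispensing or assignment date, an unused taper kit could put removal after the true last patch. The one-direction claim therefore depends on the first-use reading. Several kits per visit are also possible; weekly kits would cap the error at about a week. Both points stand.
- **Catch-all in SAP 4.2.2.** Events or medications whose status cannot be determined count as treatment emergent or concomitant. It might be invoked here, but SAP 3.2.1.2 supplies a definite date, so it does not clearly apply. It does not cover exposure at all.
- **Liver-injury stops are a weak example.** Protocol 6.3.1 keeps these subjects in the study until monitoring is complete and requires the reason for stopping in the eCRF, so a missing date is less likely. That is fair.
- **Listings.** SAP 3.1 shows dates as documented, so a blank may be visible, and the relative-day number itself does not change. But nothing marks that an exposure value or a plus sign rests on a derived date.
- **The better sources may also be blank,** above all in subjects lost to follow-up. True, and no rule can recover a date that nobody recorded.

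A reader might infer that the fallback removes Visit 9 scores from the efficacy analysis, or that TEAE and exposure tables are understated across the trial. The documents support neither. With a recorded taper-kit start the Visit 9 scores stay valid. Without one, a completer's loss is only one of two readings. Nothing shows that the last-patch date is often missing.

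**Conclusion.** The point holds as a minor one. On the first-use reading, the fallback can only date removal correctly or too early. With one kit per dispensing visit on nominal days, the error is 3–4 days if a taper-kit start is recorded, 0 to about 27 days for a maintenance withdrawal without one, and 32 days for a completer who tapers without one (36 or 39 at the visit-window limits). Smaller kits would shrink these figures.

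For withdrawals the post-removal TEAE days are lost under either wording. For completers the TEAE, medication and score consequences depend on which wording governs, while the exposure error does not. No hypothesis test is affected.

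**What to change.** Replace the fallback in SAP 3.2.1.2 with the latest documented evidence of patch use:

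1. the last end date in the eCRF drug dosing log, stating whether it is an application or a removal date, so that the extra day is added only where needed;
2. the last documented application date, for example the one collected with the PK sample at Visit 9 or the Withdrawal Visit (Protocol 10.1);
3. the last kit start date, as a floor only, and only if it is confirmed to be a first-use date.

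State that this yields the last known removal date that SAP 3.2.2 refers to. Flag derived dates in the listings and report how many subjects have one.

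The cost is one or two SAP sentences, a listing flag and a small programming change. SAP 1 allows amendments before database lock. Whether the final dosing-log end date is filled in when the termination date is missing must be checked in the eCRF. In subjects with no better record the result stays as under the current rule, and the flag will show it.

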3.2.2 Study periods

The following time periods are defined for this study.

- Screening Period:

The Screening Period starts with Visit 1 and ends the day before the date of the first patch application. This period includes Visit 2/Day 0 at which the subjects are randomized, and study medication is assigned and shipped.

- Titration Period:

The Titration Period starts at the day of the first patch application (Day 1) and ends on the day prior to Visit 6. In case of a premature withdrawal before Visit 6, the Titration Period ends at the day of the Withdrawal Visit. If the Withdrawal Visit is missing or the date of the last patch removal (or last known patch removal) is before the Withdrawal Visit, the Titration Period ends at the day of last patch removal.

- Maintenance Period:

The Maintenance Period starts at Visit 6 and ends at Visit 9. If the subject withdraws prior to Visit 9, the Maintenance Period ends at the day of the Withdrawal Visit date or the last patch removal date (or last known patch removal date), whichever is earlier.

- Taper Period:

The Taper Period starts at the date of last maintenance patch removal and ends at the day of last patch removal. If the day of last patch removal is on the date of last maintenance patch removal, i.e., no de-escalation was performed for any reason, then no Taper Period is defined for this subject.

- Treatment Period:

The Treatment Period comprises the Titration Period, the Maintenance Period, and the Taper Period, i.e., it starts with the day of first patch application and ends on the maximum end date of the Titration, Maintenance and Taper periods.

- Safety Follow-Up Period:

The Safety Follow-Up Period starts the day after the end of the Treatment Period and ends at the date of the Safety Follow-Up Visit. However, AEs starting within 30 days following the date of last patch removal will be considered for analysis, even if the start date is after the

date of last study assessment. If the subject rolls over into the RL0007 study, then the Safety Follow-up Period dates will be missing.

3.2.3 Visit mapping

The visits are planned as shown in the Protocol Table 5-1 Schedule of assessments. These visit windows were revised for the purpose of identifying important protocol deviations at visits 2, 7 and 8:

Visit	Day	Visit Window
Visit 1 (Screening)	Day -28 to Day -1	
Visit 2 (Baseline)	Day 0	+5 Days
Visit 3	Day 1	+5 Days
Visit 4	Day 8	± 1 Day
Visit 5	Day 15	± 1 Day
Visit 6 (Start of Maintenance)	Day 22	± 2 Days
Visit 7	Day 50	± 5 Days
Visit 8	Day 78	± 5 Days
Visit 9 (EoM)	Day 106	± 2 Days
Visit 10	Day 110	Visit 9 + 4 days
Safety Follow-Up	30 Days after End of Taper Period	

Analysis by visit will be done as documented in the eCRF, i.e., no visit correction will be conducted due to deviations from scheduled time points.

Assessments at premature withdrawal of the study are documented in the eCRF pages of Visit 9 (EoM/ Withdrawal). For data listings, assessments of Withdrawal Visit and of Visit 9 as scheduled will be presented separately as

- Premature Withdrawal for subjects who prematurely terminated the study
- Visit 9 (EoM) for subjects who completed the study.

Unscheduled assessments may be recorded during the study. Information collected in the log forms (e.g., AEs and concomitant medications) is included in the analysis. However, assessments at unscheduled visits will not be considered in the by-visit analysis unless data captured at these visits fall within the protocol defined visit windows (Protocol Table 5-1) and there was no corresponding endpoint data collected at the same scheduled visit. The information collected during unscheduled visits will be presented in the listings labeled as the unscheduled visit.

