3.3 Definition of Baseline values

Unless otherwise noted, baseline is defined as the last available value on or before the day of the first patch application.

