3.5.4 Full Analysis Set (FAS)

The FAS will consist of all subjects from the SS who have a valid IRLS score with a valid post-Baseline IRLS score or a valid CGI Item 1 score at Baseline paired with a valid post-Baseline CGI Item 1 score. This population is the primary population for efficacy analysis.

A valid IRLS or CGI Item 1 score at Baseline is defined as a completely answered questionnaire on or before the date of first study medication. A valid post-Baseline IRLS or CGI Item 1 score is defined as a completely answered questionnaire during the Treatment Period, i.e., measured after Baseline and on or before one day after the last patch removal.

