4.2 Handling of dropouts or missing data

Subjects who prematurely discontinue the study will be evaluated based on the data collected at each visit attended. If the premature discontinuation occurs at a scheduled visit, data collected at that visit will be summarized at the scheduled visit time point. Otherwise, the data will be attributed to the next scheduled visit for the purpose of by-visit endpoint summaries.

With respect to AEs, events with missing intensity will be assumed to be severe. Events with missing relationship to study medication per the investigator will be assumed to be related. Events with a missing answer to the question "Serious Adverse Event?" will be considered serious.

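### Do SAP 3.2.3 and SAP 4.2 put Withdrawal Visit scores in different cells of the by-visit efficacy summaries?

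*SAP*

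**What the plan says.** **SAP 3.2.3 (Visit mapping).** The general rule is "Analysis by visit will be done as documented in the eCRF, i.e., no visit correction will be conducted due to deviations from scheduled time points". The section then notes that withdrawal assessments are entered on the Visit 9 (EoM/Withdrawal) pages of the eCRF. It continues "For data listings, assessments of Withdrawal Visit and of Visit 9 as scheduled will be presented separately as" and gives two labels, one for premature withdrawal and one for Visit 9. It does not mention summaries at this point.

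**SAP 4.2 (Handling of dropouts or missing data).** "If the premature discontinuation occurs at a scheduled visit, data collected at that visit will be summarized at the scheduled visit time point". For all other withdrawals: "Otherwise, the data will be attributed to the next scheduled visit for the purpose of by-visit endpoint summaries".

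**SAP 4.2.1** does not impute efficacy assessments scheduled after withdrawal. **SAP 8.1.2 and 8.2.1** present IRLS, CGI Item 1 and RLS-6 as descriptive statistics by visit.

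**Protocol 8.6** explains why a withdrawal yields scores on any day: "Procedures for a withdrawal visit are the same as for Visit 9". **Protocol 13.3.1** used Withdrawal Visit data for the next consecutive visit.

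**SAP 5.1** describes completing titration in a parenthesis as attending Visit 5, then closes with a counting rule based on not withdrawing before the period ends.

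**The concern.** A programmer who works from the section titled Visit mapping sees three statements in a row: follow the eCRF label, withdrawal data sit on the Visit 9 page, and the two are split for listings. The natural inference is that they are not split in tables. Every valid withdrawal score would then enter the Visit 9 row, whenever it was taken. The EoM summary of both co-primary variables would become a last-on-treatment value rather than a Day 106 value, and the earlier rows would lose the same scores. The listings would show which scores came from withdrawals; the table would not.

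The study ended early and the by-visit summaries are all that remains of the efficacy analysis, so the handling of off-schedule final visits is a fair question. A second question follows. Applied literally, 4.2 sends an early withdrawal to Visit 4 or 5, where no efficacy scale is planned.

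**Working it through.** **Inputs.** Nominal days from the SAP 3.2.3 table: Visit 4 = 8, Visit 5 = 15, Visit 6 = 22, Visit 7 = 50, Visit 8 = 78, Visit 9 = 106. Visit windows are ignored. Under SAP 3.3, "Unless otherwise noted, baseline is defined as the last available value on or before the day of the first patch application", so a Day 1 score is Baseline and the first post-Baseline day is Day 2. Withdrawal days before EoM are therefore Days 2-105, which is 105 - 2 + 1 = 104 days.

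**Placement of a withdrawal score**

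| Day of withdrawal | Days | SAP 4.2 | 3.2.3 read alone |
|---|---|---|---|
| 2-8 | 7 | Visit 4 | Visit 9 |
| 9-15 | 7 | Visit 5 | Visit 9 |
| 16-22 | 7 | Visit 6 | Visit 9 |
| 23-50 | 28 | Visit 7 | Visit 9 |
| 51-78 | 28 | Visit 8 | Visit 9 |
| 79-105 | 27 | Visit 9 | Visit 9 |

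- Readings differ: 7 + 7 + 7 + 28 + 28 = 77 days; 77/104 = 74.0%.
- Readings agree: 27 days; 27/104 = 26.0%.
- Label minus actual day on Days 2-78 if placed at Visit 9: 106 - 78 = 28 to 106 - 2 = 104 days.
- Day 40 example: 106 - 40 = 66 days late at Visit 9, against 50 - 40 = 10 days at Visit 7.
- Days 2-15 moved to Visit 6, the first visit with an efficacy scale: 22 - 15 = 7 to 22 - 2 = 20 days.
- Longest lag under 4.2 at visits where the scales are planned: 22 - 2 = 20 (Visit 6), 50 - 23 = 27 (Visit 7), 78 - 51 = 27 (Visit 8), 106 - 79 = 27 (Visit 9).

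**Effect on a mean.** Let n_c and m_c be the number and mean of scores that 4.2 puts at Visit 9, and n_w and m_w those of withdrawals on Days 2-78. Reading 3.2.3 alone would shift the EoM mean by n_w/(n_c + n_w) x (m_w - m_c). The documents give none of these four quantities, so the shift cannot be computed. If nobody withdrew before Day 79, n_w = 0 and the shift is zero.

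**Which rule governs.**

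1. Section 4.2 deals with premature discontinuation and states that its purpose is by-visit endpoint summaries. That is the exact question.
2. The general rule in 3.2.3 explains itself as not correcting for off-schedule timing. That covers a Visit 7 held early or late. A withdrawal visit is not a mistimed Visit 9.
3. The withdrawal paragraph in 3.2.3 says where data are entered and how listings are labelled. It sets no rule for tables.
4. Protocol 13.3.1 used the next consecutive visit, which matches 4.2 for withdrawals between visits. The model it served is no longer run, but the intent is clear.
5. SAP 4.2.1 leaves later scheduled visits empty. Showing a Day 40 score at Day 106 would fit poorly with that.

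**Days 2-15.** A score must still be valid under SAP 3.5.4, that is, "measured after Baseline and on or before one day after the last patch removal". It can be shown at Visit 6, the next visit with that scale, or on its own row. Both are defensible in a descriptive table.

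**SAP 5.1.** Titration ends the day before Visit 6 (SAP 3.2.2), so the parenthesis could matter only for withdrawals on Days 16-21, which is 6 days. The closing rule of 5.1 settles them: a subject who withdraws before the period ends has not completed it.

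**The case for a change.** The best case for an edit is that intent which can be inferred is not the same as a written instruction. The Visit 9 row carries the co-primary time point, the situation was foreseeable in a study that stopped early, and one sentence would remove the doubt at no cost. It is true that the sections do not cite each other, that 3.2.3 can be misread, and that 4.2 does not say what happens when the next visit does not include the scale.

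What does not stand is that a result depends on it. A cross-reference would only confirm the rule that 4.2 already states. The 74.0% counts calendar days and would measure impact only if withdrawals were spread evenly over time. The reach is also narrower than all the rating scales: mMIDI, C-SSRS and RLS-QoL are only listed, and the listings already label premature withdrawal.

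An edit is not free of risk either. The question of unplanned visits is not confined to efficacy. By the visit lists in Protocol 8.3.1 to 8.3.3, ECG and hormones are planned on treatment only at Visit 9, and vital signs and laboratory tests at Visits 6 and 9. If 4.2 is taken to cover safety data, it sends withdrawal ECG and hormone results to visits without them on all 77 of Days 2-78. For vital signs and laboratory data it does so on 14 + 56 = 70 days (Days 2-15 and 23-78). A sentence in 3.2.3 that routed every Withdrawal Visit assessment through 4.2 would therefore create ECG and hormone rows at Visits 4-8, where none are planned.

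**Conclusion.** No change to the plan follows. The apparent conflict is a missing cross-reference between a general rule and a specific one. The specific rule, 4.2, addresses these summaries directly and is supported by Protocol 13.3.1 and SAP 4.2.1. An analyst who follows it obtains sound descriptive tables. The Day 2-15 question is a gap of 14 nominal days with two reasonable answers and no clear gain from fixing one in advance. The 5.1 parenthesis is a loose phrase that the same section corrects.

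This rests on three assumptions: nominal visit days without windows, 4.2 taken as the governing rule, and efficacy output that stays descriptive as SAP 8.1.2 and 8.2.1 state. If a test or an EoM estimate were reinstated, the placement of withdrawal scores would matter more and would deserve an explicit sentence.
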